Health Status: The *Cumulative Illness Rating Scale (CIRS)*^{135,136} was designed for use with frail nursing facility residents. CIRS will be obtained at baseline. It contains ratings of both illness severity and comorbidity. Residents are evaluated based on 13 organs or systems and a psychiatric/behavioral rating. CIRSSs ratings correlated with medication use and predicted mortality, hospitalization and disability.^{135,136}

Facility and Staff RE-AIM Measures

The Environment Assessment (Effectiveness; Adoption; Maintenance): includes 24 items that impact care of residents with BPSD (e.g., outdoor spaces are available). Items are scored as present or not present and summed. There was prior evidence of inter-rater reliability and validity based on hypothesis testing.^{8 22,23,137}

Policy Assessment (Effectiveness; Adoption; Maintenance): includes 24 items that reflect policies that support behavioral approaches for BPSD (e.g., policies on use of restraints). Items are scored as present or not present and summed. There was prior evidence of inter-rater reliability and validity.^{8 22,23,137}

The Care Plan Checklist for Evidence of Person Centered Approaches for BPSD (Effectiveness; Adoption; Maintenance) is used to evaluate care plans for approaches that address common BPSD (apathy, agitation, inappropriate/disruptive vocalizations, aggression, wandering, repetitive behaviors, resistance to care, and sexually inappropriate behaviors).

Knowledge of Behavioral Interventions For BPSD Test (Implementation; Receipt) is a 10-item multiple choice test that evaluates staff knowledge. Evidence of test-retest reliability was supported with correlations of .92 and validity with significant associations between knowledge and use of behavioral interventions for BPSD.¹³⁸

Use of Behavioral Interventions for BPSD (Implementation; Enactment) is a reliable and valid 8-item observation measure that assesses if nursing assistants implement appropriate interventions to prevent or manage BPSD when interacting with a resident during routine care.¹³⁸

Resident RE-AIM Measures

Behavioral Symptoms (Effectiveness): Depressive symptoms will be measured using the *Cornell Scale for Depression in Dementia (CSDD)*^{139,140}. CSDD is a 19 item survey that assesses depressive symptoms in individuals with dementia. There is evidence of reliability and validity of the CSDD.¹³⁹⁻¹⁴¹ Aggressive and/or resistive behaviors during care activities will be measured using the *Resistiveness to Care Scale*,¹⁴² a reliable and valid 13 item Likert scale that assesses residents' behaviors during activities of daily living. Agitated

behaviors will be measured using the *Cohen-Mansfield Agitation Inventory (CMAI)*,^{143,144} a survey of disturbing behaviors commonly found in residents with dementia. The 14 item version CMAI uses a 5-point Likert scale to rate the frequency of behavioral symptoms.^{144,145} Prior use supported evidence of reliability and validity.^{144,145}

Function (Effectiveness): *The Barthel Index (BI)*¹⁴⁶ is a 10 item measure of performance of activities of daily living with evidence of internal consistency, inter-rater reliability and validity.^{146 147} Items are weighted to account for the amount of assistance required. A total score of 100 indicates complete independence.

Quality of Life: will be measured using the *Quality of Life-AD (QoL-AD)*¹⁴⁸ scale. The QoL-AD is a 13 item reliable and valid instrument designed to rate the resident's quality of life from the staff perspective. Examples of items include physical condition, mood, relationships and participation in meaningful activities. Ratings are obtained on a 4 point scale (1= poor to 4=excellent) and total scores range from 13-52.¹⁴⁸

Adverse Events (Effectiveness): will be based on data obtained from medical records and designated individuals within the facilities (e.g., quality assurance nurse). Adverse events will include falls and transfers to hospitals or emergency rooms and physical restraint use. Baseline will include the four months prior to treatment implementation; 4 month will include those between baseline and 4 months; and 12 month those that occur between 4 months and 12 months post implementation of the intervention. Restraint use will be based on the reliable Minimum Data Base 3.0 definition of assessment for use of restraints.¹⁴⁹⁻¹⁵¹

Data Analysis:

Aim 1: To implement and test the implementation of EIT-4-BPSD.

Research question: Do facilities exposed to EIT-4-BPSD demonstrate evidence of implementation at 12 months evaluated by Reach, Effectiveness, Adoption, Implementation, and Maintenance (RE-AIM) Criteria?³³

Reach: *To facilities:* Descriptive statistics will describe total number of eligible facilities across both states at the time of recruitment and the percentage of eligible facilities volunteering to participate by state and overall. In addition, we will compare facilities (by state and overall) willing to participate versus those that were not with regard to facility characteristics (e.g., size, profit status). We will also compare facilities expressing a willingness to participate versus those that do not using publically available Nursing Home Compare data.¹⁵² *To staff:* We will evaluate reach to staff in terms of percentage of staff exposed to education (# exposed/total number of staff) in EIT-4-BPSD and EO facilities. *To residents:* Using the Care Plan Checklist for Evidence of Person-Centered Approaches for BPSD we will evaluate the percentage of all residents (using de-identified care plans) living in EIT-4-BPSD facilities that have at least 1 person-centered approach for BPSD.

Effectiveness:

Effectiveness will be based on testing the following *hypotheses*.

H1: Resident level: Residents in EIT-4-BPSD facilities will experience less BPSD, maintain or improve function, have reduced use of psychotropic medications, experience fewer adverse events and have improved quality of life compared to residents in EO facilities.

H2: Facility-level: EIT-4-BPSD facilities will demonstrate improvements in Environment and Policy assessments that support behavioral approaches for BPSD, and will have a greater percentage of residents with behavioral approaches addressed in care plans at 12 months when compared to EO facilities.

Descriptive statistics including measures of central tendency, dispersion and appropriate visualization approaches (e.g., box plots and spaghetti plots) will be performed on each outcome variable for residents and facilities. This will be done to ascertain distributional characteristics and ensure that the assumptions (e.g., normality) associated with the planned statistical procedures are met. When necessary, transformations will be performed. All analyses will be done using an intent-to-treat philosophy. Baseline characteristics (both resident level and facility level) will be compared between intervention and control groups and the relevant variables (e.g., age) that differ by group will be included as covariates in hypotheses testing. In particular we will utilize constructs known to correlate with BPSD including gender, pain, health status and cognitive and functional impairment. Linear mixed models (LMMs)¹⁵³ for longitudinal data (baseline, 4 and 12 months) will be used to assess the intervention effect on continuous outcomes (i.e., function, behavioral symptoms, and quality of life) accounting for clustering of residents that may occur within the same facility and correlations between repeated measurements of each resident. Mixed-effect Poisson regression [i.e., Generalized Linear Mixed Model

(GLMM)] will be conducted to assess the effect of the intervention on count outcomes (i.e., number of adverse events including number of falls, hospitalizations and emergency room visits, restraint use). The fixed effects included in the models will be treatment group (EIT-4-BPSD versus EO), time (baseline, 4 and 12 months), group-by-time interaction term and the aforementioned relevant covariates (e.g., age). Random effects will include facilities and residents.

The hypothesis will be tested by evaluating the interaction term for each outcome variable. Similar LMMs will be used to compare changes in facility level measures (i.e., environments, policies) from baseline to 12 months with only facility included as random effects. For each hypothesis, exploratory analyses will be performed to assess model assumptions. Post-analysis diagnostic measures (e.g., residuals) will be explored to assess model fit. All tests will use a 5% significance level. The use of LMM will provide flexibility with regard to assumptions related to the covariance structure of the residuals and the presence of missing data for the repeated measures.¹⁵⁴ Missing data. In prior research we had 20% rate of attrition at the resident level and 10% of facilities.^{22,23} If there is significant dropout, we will identify baseline characteristics that differ between persons or facilities that drop out. Maximum likelihood methods will be used for primary analyses, which address non-informative dropout (missing at random [MAR]). If "informative" dropout appears possible, we will consider sensitivity analyses that involve adding these relevant baseline covariates to make the MAR assumption more plausible.¹⁵⁵ Qualitative data will be collected to inform effectiveness outcomes.

Adoption: Staff Adoption: Descriptive statistics will be done to evaluate the number of Internal Champions and Stakeholder team members participating in initial face-to-face training and monthly meetings among the 25 facilities randomized to EIT-4-BPSD. We will also consider improvement in scores on the Use of Behavioral Interventions for BPSD measure at each testing time point as evidence of adoption among staff. Facility Adoption: Facility adoption will be based on changes in environments, policies, and care plans of residents at 4 and 12 months post implementation of EIT-4-BPSD such that there is at least 1 item changed in each assessment area. Further we will describe differences among EIT-4-BPSD facilities that demonstrate adoption (based on changes in environments, policies and care plans) early (the first 4 months) versus late adopters (between 5-12 months) versus those that are non-adopters (no change by 12 months). Predictors such as facility characteristics will be compared across the three potential times of adoption (early, late, nonadopters).

Implementation: Delivery/Dosage: We will describe the number of treatment facilities that are exposed to the first EIT-4-BPSD training session and the number of EO facilities and staff exposed to education session. In addition, we will measure evidence of delivery for each step of the EIT-4-BPSD intervention. Step 1: Percent of environmental and policy assessments completed. Step 2: Percentage of staff exposed to education. Step 3: Percentage of residents with evidence of person-centered approaches to BPSD in care plans. Step 4: Description of mentoring and motivating activities (e.g., participation in contests); number of observations of staff-resident interactions (Use of Behavioral Approaches for BPSD measure) at 0-2, 4-6, and 10-12 months; number of telephone conferences requested. Receipt: Descriptive statistics of staff Knowledge of Behavioral Interventions for BPSD Test with mean scores of 80% or greater providing evidence of receipt. We will also compare differences in mean scores of percentage correct on the Knowledge of Behavioral Interventions for BPSD Test between EIT-4-BPSD facilities and EO facilities. Enactment: Descriptive statistics reflecting the percentage of care interactions in which person-centered approaches for BPSD in EIT-4-BPSD facilities are provided based on the Use of Behavioral Approaches for BPSD measure. This is done as part of Step 4 within EIT-4-BPSD at baseline (0-2 months), 4-6 and 10-12 months post implementation of EIT-4-BPSD. This will provide evidence that the staff enacted person centered behavioral approaches to address BPSD.

Maintenance: Long term Attrition: We will track facilities that withdraw from the study within 12 months (as well as reasons for attrition). We will compare EIT-4-BPSD facilities with EO facilities to determine if there is a differential rate of attrition. Maintenance of environment and policy changes and inclusion of person-centered approaches for BPSD in care plans will be examined at 24 months post implementation of EIT-4-BPSD. Evidence of maintenance will be based on maintaining or improving Environment and Policy assessments and percentage of residents with evidence of person-centered approaches for management or prevention of BPSD in their care plans. LMMs will be used to compare changes in facility level measures from baseline to 24 months with facility included as random effects. Time will be included and recorded accordingly. Comparison of outcomes at 12 and 24 months will be examined to determine maintenance over that time period.

Primary Aim 2: Evaluation of the Feasibility, Utility and Cost in EIT-4-BPSD Facilities

Using descriptive and qualitative data from focus groups (held following the intervention) we will evaluate use of the EIT strategy and our participatory implementation process with the stakeholder team and additional facility staff. We will determine the cost of the implementation process using an activity-based costing method.

Aim 2: To evaluate the use of EIT and our participatory implementation process.

Findings will be descriptive and considered at the individual facility level and across all treatment facilities. Data will include a summary of information obtained during the intervention including: (1) ideas generated from the Brainstorming sessions¹⁵⁶; (2) themes identified in the Affinity Diagrams; and (3) "drivers" identified to overcome challenges to implementing person-centered behavioral approaches to BPSD via implementation of the EIT-4-BPSD (Interrelationship Diagraphs). We will quantify similarities across facilities to note the most common themes and drivers identified and establish best practices. We will also have facilities evaluate their goal achievement at 12 months (Appendix B).

Focus groups will be conducted at the end of the intervention activities in order to better understand the implementation process¹⁵⁷. The stakeholder team and additional facility staff (e.g., nursing, administrative, activities, therapy, and social work) will be invited to participate in a 60 minute focus group discussion at 12 months post implementation of EIT-4-BPSD. Groups will consist of a maximum of eight staff and stakeholder team members per facility¹⁵⁸. Eligibility criteria include membership on the stakeholder team or working in the facility over the past year. Stakeholders/staff will be excluded from the study if they are less than 21 years of age. Demographic information will be obtained from participants to describe the group composition. (See Human Subjects section for recruitment /consent processes.)

Drs. [name], [name], [name], and [name] will moderate the focus groups through a carefully designed series of questions that engage the group and then progress toward the most substantive areas of inquiry^{159,160}. All moderators are experienced in leading focus groups with staff in long term care facilities. Key elements of the inquiry address the RE-AIM framework(see Appendix G, Focus Group Interview Guide). Data collection will end when saturation of findings has been achieved (i.e., when no new barriers, facilitators or other insights are gleaned from incoming data) or all 25 treatment facilities completed. A minimum of 6 focus groups will be conducted. Sessions will be audio-recorded and transcribed verbatim.

A team approach to data collection and analysis will be used. Drs. [name] and [name] will lead the Maryland effort and Drs. [name] and [name] will lead in Pennsylvania. Site leaders will be responsible for ongoing review of transcripts in order to ensure the quality of moderation. Data entry and analysis will be done using standard Word documents. Verified "clean" transcripts (confirmed for accuracy of transcription and purged of identifiers) will be shared on a secure, password protected data management site. Within- and across-group analyses will be completed using techniques of conventional content analysis¹⁶¹. This analytic approach produces a taxonomy of responses to targeted questions in the discussion guide (e.g., facilitators, barriers) as well as rich description of the process of implementation and resultant outcomes.

Analytic sessions will begin after two focus groups have been transcribed/verified. The full team will meet to share preliminary coding insights and develop a standardized codebook. Drs. [name], [name], [name] and [name] will code the full transcript individually and inter-rater reliability will be evaluated. The codebook will be refined and iterative double-coding/team meetings will proceed until a satisfactory level of agreement is achieved (Kappa Coefficient ≥ 0.8). As data collection/coding proceeds, the four investigators will meet via conference call at least bi-weekly. In the event that consensus cannot be reached at any time during the analysis process, the four investigators will be led in adjudication by [name]. Findings will be shared with stakeholder teams and consultants to confirm/refine insights and integrate their knowledge of the environment and intervention related activities. The qualitative findings will not be transformed for integration in quantitative analyses, but we will use descriptive statistics to summarize patterns in the categorical findings in the taxonomy. The final stage of analysis involves examining the qualitative findings for "fit" with the quantitative findings. Variations in qualitative findings may be related to contextual features or implementation processes at a given facility. This approach permits integration of qualitative findings with other sources of formative evaluation data to understand EIT-4-BPSD implementation and outcomes.

Four quality criteria for establishing the trustworthiness of the qualitative data will be addressed¹⁶²: (1) Credibility (i.e., confidence in the 'truth' of the findings) is enhanced by the team's methodological expertise and familiarity with the facilities; rigorous analytic approaches; the use of a detailed audit trail; triangulation through use of multiple facilities; and iterative questioning; (2) Transferability (i.e., applicability of findings to other contexts) will be established through rich description of the facilities and consideration of the similarity

with other facilities in these states and nationally; (3) Dependability (i.e., application of methods that can be replicated) will be based on our detailed methodological approach, coding dictionaries and audit trail; (4) Confirmability (i.e., the extent to which the findings represent the voice of participants) will be enhanced through the use of our consultants both of whom have extensive knowledge of the long term care environment and by reviewing and confirming the findings with each stakeholder team (in written or verbal format).

In addition to obtaining qualitative findings, we will determine the costs of the implementation process (Appendix H) with regard to the services of the Research Nurse Facilitator, the amount of time the internal champion/stakeholder team spends in training and working with the Research Nurse Facilitator, the amount of time for staff education and time spent by the internal champion to implement the 4 steps of EIT-4-BPSD. An activity-based costing method will be used which includes: (1) gathering resources used in the implementation process such as personnel, supplies and other expenses; (2) establishing the amounts used of these resources; (3) multiplying the amounts of resources used by the unit cost to determine the cost associated with the resource; (4) tracking the time spent by each individual on activities related to implementation of EIT-4-BPSD and multiplying this by the hourly compensation associated with the individual; and (5) summing costs across all components of the implementation process to determine the total cost of implementation. Study timeline is described in Table 3.

Table 3: Study Timeline

Table 3: Time Line (Treatment and Control facilities will be run simultaneously). Cohorts will be run in groups of 16-20 facilities with a total of three cohorts run over the 5 year study period. The two Research Nurse Facilitators will be working with a total of 8-10 EIT-4-BPSD facilities per cohort group such that each will be responsible for 4-5 EIT-4-BPSD facilities during the cohort period.	
Study Months	Activities
STUDY ACTIVITIES: Recruitment of Facilities/Randomization (16-20 facilities/cohort with a total of 50 facilities- 25 from each state)	
Month 1-4 Initial Planning/Set Up	IRB/Staff training; facility recruitment; Cohort 1 Coordination with facilities; EIT-4-BPSD planning for training and identification of Internal Champions; listserv of Internal Champions and Stakeholders for weekly emails. EO planning for in-service.
Month 5-17 Cohort 1 Intervention	EIT-4-BPSD Intervention: 4-5 from Maryland; 4-5 from Pennsylvania; Implementation of Steps of EIT-4-BPSD; Recruitment of 12-13 residents per facility, complete assessments of residents and facilities including cost data.
	EO Intervention: 4-5 from Maryland; 4-5 from Pennsylvania; Coordinate and provide the educational intervention; Recruitment of 12-13 residents per facility and complete assessments of resident and facilities.
Month 18-20 Cohort 2 Set Up	Cohort 2-Coordination with facilities; planning for face-to-face training; and identification of Internal Champion.
Month 21-33 Intervention	EIT-4-BPSD Intervention: Same process as for Cohort 1; 18 and 24-month maintenance data collection for Cohort 1 (months 23 and 29)
	EO Intervention: Same process as for Cohort 1
Month 34-36 Cohort 3 Set Up	Cohort 3-Coordination with the Facilities; planning for face-to-face training and identification of Internal Champion.
Month 37-49 Intervention	EIT-4-BPSD Intervention: Same process as for Cohorts 1 and 2; 18 and 24 month maintenance data collection for Cohort 2 (months 39 and 45)
	EO Intervention: Same process as for Cohorts 1 and 2
Month 50-60	18 month maintenance data collection for Cohort 3 (month 55); Completion of data entry, analysis and manuscript development;

Strengths and Limitations: We included facilities from two states and residents who have evidence of BPSD. Thus findings cannot be generalized to all residents and all nursing homes. Due to the limitation on recruitment numbers this study does not provide a true reflection of reach, but provides data to inform future dissemination research. We recognize that all facilities are different with unique challenges. We use the EIT to allow flexibility in implementation and have included known factors that may influence study outcomes such as size and staffing. There may be other factors we have not considered. To overcome this limitation we will adjust for clustering and resident characteristics. Potential challenges include participation of facilities, engagement of Internal Champions and stakeholders, staff turnover, and loss to follow up of residents. We anticipate these challenges and are prepared to retrain staff if there is turnover and will over sample to address loss to follow up. We have a highly qualified and experienced team with members who have successfully engaged administration and staff in the planning, development, training and implementation of similar care related interventions. Despite limitations, EIT-4-BPSD has the potential to make a significant impact on practice in our nation's 15,633 nursing homes by providing guidance on how to implement person-centered behavioral approaches for BPSD, the ultimate goal of the National Partnership.

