Real World Experience and Pilot Testing EIT-4-BPSD: Our team has expertise with regard to clinical work ([name], [name], [name]), administration ([name]) and regulations ([name]), and implementation of relevant innovative approaches to care (all investigators) in nursing homes. In addition, we have expertise in the education of minorities and nursing assistants([name], [name], [name], [name], [name]) and using qualitative methods ([name], [name], [name]) (see biosketches). We have pilot tested the EIT-4-BPSD in two facilities (one in Maryland and one in Pennsylvania) for feasibility and demonstrated that sites are willing to identify a Champion and Stakeholder team, engage in monthly face-to-face meetings (100% participation of stakeholders) and weekly email interactions (100% participation). We implemented all components of the intervention, recruited residents (recruitment rate of 50%) and completed measures without being burdensome to residents or staff. Building on our extensive preliminary work we will test EIT-4-BPSD in 50 nursing homes in Maryland and Pennsylvania.

Methods

Design: To achieve our Aims we will use a Hybrid III pragmatic cluster randomized clinical trial³² for two reasons: (a) implementation of EIT-4-BPSD requires a facility-wide approach; and (b) we need to prevent treatment contamination that might occur if we randomized within sites. Fifty nursing homes will be randomized to treatment (EIT-4-BPSD) or Education-Only Control (EO) using permuted-block randomization. Assignment will be concealed until after the facility consents to participate. Outcomes at the resident and facility level will be evaluated. Resident outcomes will be obtained at baseline, 4 and 12 months post implementation of the intervention. Facility outcomes will be obtained at baseline and 12 months post initial implementation. We will also examine Maintenance in EIT-4-BPSD facilities at 24 months post implementation.

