Once the nursing facility expresses an interest in participating in the study, the facility will be randomized to one of three cohort groups and then randomized to EIT-4-BPSD or EO. We will implement EIT-4-BPSD in 8-10 facilities and the EO intervention in 8-10 facilities during each cohort period. We recognize there will be a period of time between recruitment and implementation of study related activities and will keep facilities updated. In addition, we will maintain a waiting list of interested facilities in the event that some volunteer facilities decide not to participate (their data will be included in terms of Reach).

Resident Participants: We will keep our resident enrollment criteria to a minimum to increase external validity. Residents will be eligible to participate if they: (a) are living in a participating nursing home; (b) are 55 years of age or older; (c) have a history within the past month of exhibiting at least one BPSD; (d) have cognitive impairment as determined by a score of 0-12 on the Brief Interview of Mental Status (BIMS);¹²² (e) are not enrolled in Hospice; and (f) are not in the nursing facility for short-stay rehabilitation care. We will obtain a list of all eligible residents from a designated staff member and randomly approach each resident until 12-13 residents per facility are recruited by research assistants (RAs) (N= 625 residents). This sampling approach is used to assure variability and equal participation from each nursing facility in the study. Based on our prior research and recent data from the most recent Nursing Home Compendium¹²³ we conservatively anticipate that 25% to 30% of residents will be eligible.^{123,124} We are confident we will be able to recruit 12-13 residents per facility.^{8,77,125} See the Human Subjects section for details of the consenting and recruitment process.

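### No stratification by state is stated, although Table 3 plans a fixed state-by-arm layout, and neither state nor cohort is a prespecified model term

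*Combined protocol and SAP*

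**What the plan says.** **Allocation.** Methods, Design: "Fifty nursing homes will be randomized to treatment (EIT-4-BPSD) or Education-Only Control (EO) using permuted-block randomization". Methods, Setting, adds the order: "the facility will be randomized to one of three cohort groups and then randomized to EIT-4-BPSD or EO". It also gives the numbers: "We will implement EIT-4-BPSD in 8-10 facilities and the EO intervention in 8-10 facilities during each cohort period". No block size is given, and state is not mentioned at either step.

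**Planned layout.** Table 3 (Study Timeline) plans "16-20 facilities/cohort with a total of 50 facilities- 25 from each state". For Cohort 1 it lists "EIT-4-BPSD Intervention: 4-5 from Maryland; 4-5 from Pennsylvania" and "EO Intervention: 4-5 from Maryland; 4-5 from Pennsylvania"; later cohorts follow the same process. It adds that "The two Research Nurse Facilitators will be working with a total of 8-10 EIT-4-BPSD facilities per cohort group", which is 4-5 homes for each Facilitator.

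**Analysis.** Data Analysis, Effectiveness: "The fixed effects included in the models will be treatment group", then time, group-by-time and relevant covariates, with facility and resident as random effects. The hypothesis test is on the group-by-time term. Covariates are the relevant baseline variables found to differ between arms. State is among the facility descriptors collected so that confounding can be considered. Cohort appears nowhere in the analysis.

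**The concern.** The allocation text and Table 3 do not match. A permuted block that ignores state balances the arms in total but not within each state, so the planned cells would not be assured.

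The covariate rule then misfires in both cases:

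- If state is stratified, as Table 3 implies, it will not differ between arms and the rule excludes it. The same holds for cohort, which is balanced at 8-10 homes per arm. The analysis would then omit the factors on which the randomisation was restricted, making the standard error of the arm contrast too large and the test conservative.
- If state is not stratified, whether it is adjusted for depends on how the realised allocation looks.

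A main effect alone would do little in either case. The tested term is a difference in change over time, so a state or cohort difference in change is removed only by an interaction with time.

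**Working it through.** **1. Does the planned layout add up?** Inputs from Table 3: 50 homes, 25 per state, two arms, three cohorts of 16-20.
25 / 2 / 3 = 4.17 homes per state, arm and cohort. Cells of 4-5 are feasible, for example with cohorts of 16 + 16 + 18 = 50. The plan's figure is reproduced.

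**2. How often would allocation that ignores state give it?** Assume each cohort is split evenly by state and has equal arms. The number of Maryland homes in the EIT-4-BPSD arm is then hypergeometric, and all four state-by-arm cells must be 4 or 5.

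| Cohort size | Calculation | Probability |
|---|---|---|
| 16 | C(8,4)² / C(16,8) = 4,900 / 12,870 | 0.381 |
| 18 | 2·C(9,4)·C(9,5) / C(18,9) = 31,752 / 48,620 | 0.653 |
| 20 | C(10,5)² / C(20,10) = 63,504 / 184,756 | 0.344 |

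All three cohorts (16, 16, 18): 0.381² × 0.653 = 0.095. Cohorts of 16, 17 and 17 give 0.050. If assignment to cohort also ignores state, the figure is 0.006.

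**3. Sensitivity to block size and order of entry** (simulation, 40,000 runs, one 16-home cohort):

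- random order, blocks of 2 or 4: 0.38; blocks of 6: 0.23
- alternating states, blocks of 2, 4 or 6: 0.27, 0.35, 0.21
- all of one state entered first, blocks of 2 or 4: 1.00; blocks of 6: 0.36

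**4. Imbalance over the whole trial.** With 25 homes per state and per arm, P(k Maryland homes in EIT-4-BPSD) = C(25,k)² / C(50,25). A 12/13 split has probability 0.43. A split of 15:10 or worse has probability 0.26.

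**5. Cost of omitting strata, facility outcomes.** Let R² be the share of between-facility variation in change that the strata explain. The documents give no value, so 10%, 20% and 30% are assumed. SE inflation = 1/√(1 − R²). Actual size of a nominal 5% test = P(|t| > 2.011 × inflation) on 48 df.

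| R² (assumed) | SE inflation | Actual size | Power, if 80% when adjusted |
|---|---|---|---|
| 10% | 5% | 3.9% | 77% |
| 20% | 12% | 2.9% | 73% |
| 30% | 20% | 2.0% | 68% |

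**6. Cost of omitting strata, resident outcomes.** Sample Size gives ICC 0.02 and 500 residents after attrition, or 500 / 50 = 10 per home. Assume the same ICC applies to change. Variance of a facility mean, in units of total variance: 0.02 + 0.98/10 = 0.118. Strata can act only on the 0.02. SE inflation = √(0.118 / (0.118 − 0.02·R²)):

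- R² 10%: √(0.118/0.116) = 1.009
- R² 20%: √(0.118/0.114) = 1.017
- R² 30%: √(0.118/0.112) = 1.026

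**7. Cost of including them.** State takes 1 df and cohort 2, so facility-level df fall from 48 to 45 and the critical t rises from 2.011 to 2.014.

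**The case against.** The strongest reply is that unstratified allocation is inferred from silence. The documents neither affirm nor exclude strata, and Table 3 suggests that balance by state was intended. On that reading the randomisation is sound and only its description is incomplete. This is fair: the probabilities in steps 2 to 4 apply only if state was ignored. It does not rescue the analysis, because a stratified state would then be dropped by the covariate rule.

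Even if state was ignored, an evenly split cohort of 18 fits more often than not, and entering one state first in small blocks can guarantee the fit. The 9% requires all twelve cells to be right, and missing by one home is mainly a workload matter. These points stand. The low figure describes the whole trial, not any one cohort.

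State is also partly handled, since it is collected with confounding in mind and a 15:10 split could bring it in as a covariate. As written, though, its inclusion is data-driven and no state-by-time term is mentioned.

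A reader might infer more than the documents support:

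- **That cohort confounds the comparison.** Arms are randomised within cohort, 8-10 homes each, and run at the same time. Omitting cohort costs precision only.
- **That the 22% fall in antipsychotic use took place across the cohorts.** The Significance section dates it from 2011 to 2015, before the trial was funded in August 2016. No figure is given for change during the cohorts.
- **That state stands for a different Facilitator or a different regulatory regime.** Neither is stated; both would be assumptions. Facilitators serve only EIT-4-BPSD homes, so they are part of that intervention and cannot be balanced across arms.
- **That chance imbalance by state invalidates the test.** It does not; the randomised test remains valid.

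**Conclusion.** The point holds as an inconsistency in the design text together with a gap in the analysis. The stated allocation does not assure the state-by-arm layout that Table 3 plans. The covariate rule leaves out cohort and any other factor balanced by design, and lets state in only after the data have been seen.

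The consequence is modest. Omitting the strata makes the test conservative and costs some power, mainly for the environment, policy and care-plan outcomes; for resident outcomes the loss is slight. These sizes rest on the assumed R² of 10-30% and, for residents, on the ICC of 0.02 applying to change. If state was in fact ignored at allocation, there is also about a one-in-four chance of a 15:10 or worse split by state. The documents do not show that the treatment comparison is biased.

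**What to change.** 1. State in the Design section that the permuted blocks are stratified by state within cohort, as Table 3 implies, and give the block sizes. Stratum and block sizes should match (for example 8 homes per stratum with blocks of 2 or 4), so that the 4-5 layout is certain.
2. Prespecify state, cohort, state-by-time and cohort-by-time as fixed effects in the facility and resident models, whether or not they differ between arms at baseline.
3. If Facilitators are to be assigned by state, say so, and show the treatment effect by state as a descriptive check.

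The cost is a revised randomisation list and model wording, plus about 3 facility-level degrees of freedom per follow-up time. No extra homes, residents or staff are needed. If homes have already been allocated, item 2 can still be adopted, provided it is fixed before outcome data are seen by arm.
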